 - HAQ response at 28 weeks after randomization and at w104
2. Radiographic progression: X-ray evolution at w52 and w104 compared to BL as reviewed and evaluated by the central team.
3. Side effects: (S)ARs from BL until w104
4. To evaluate the primary outcome using the DAS28ESR instead of the DAS28CRP.

Other secondary, exploratory outcome measures:

1. Clinical effectiveness:

A) In the randomized early insufficient responder population (w8-w32) with or without accelerated access to a six-month course of etanercept.

Effectiveness:

- AUC of DAS28CRP/DAS28ESR during 28 weeks after randomization
- Time to first remission during 28 weeks after randomization
- Sustained remission = remission for at least 24 weeks (BL-w104).
- Number of treatment changes, number of patients able to follow the protocol, number of patients using biologicals and/or GC at 28 weeks after randomization and at w104.
- Cumulative doses of GC and analgesic use at 28 weeks after randomization and at w104.

B) In the complete study population, including the randomized groups of insufficient responders, each completed with an early responder control population.

Effectiveness:

- Sustained remission = remission for at least 24 weeks (BL-w64, BL-w104, w64-w104).
- Number of treatment changes, number of patients able to follow the protocol, number of patients using biologicals and/or GC throughout the entire study

- Cumulative doses of GC and analgesic use throughout the entire study
- 2. Treatment response in terms of PROs:
 - Patient acceptable symptom state (PASS) and RA Impact of Disease (RAID) at 28 weeks after randomization and at w104
 - PASS at w64 and w104.
 - RAID at w 64, 104.
- 3. Cost-effectiveness:
 - WPAI / EQ5D questionnaire at 28 weeks after randomization and at w104
 - Per-protocol and out-of-protocol medication use as well as the number of outpatient visits and occasional hospitalization

[figure not shown]
Depending on the clinical results of the trial, a health economic analysis may be justified. This could be part of a health technology assessment project at KCE. Quality of life data as well as the national number of the participating patients are collected in this trial to facilitate a possible economic analysis.

3 Study design

Overall design

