The randomization scheme

Patients included in the trial and not achieving low disease activity (DAS28CRP \leq 3.2) between w8 and w32 or remission (DAS28CRP $<$ 2.6) at week 32, will be randomly assigned to one of two treatment groups (1:1 allocation):

- Group 1 stepping up to a combination of MTX with leflunomide as described in the standard COBRA-Slim strategy, or
- Group 2 receiving accelerated access to a 6 months course of etanercept (defined as etanercept or its biosimilars as marketed and reimbursed in Belgium) besides continued MTX therapy.

Randomization will be done electronically within the e-CRF whenever a patient is considered an insufficient responder within the time window from w8 until w32 included.

The randomization process will be balanced on the margins (minimization) according to time-point of randomization, BL disease activity and RF/ACPA status.

Patients who are not considered insufficient responders within the accelerated access period will be further followed in the protocol.

Method of implementing the allocation sequence

Each clinical site will be assigned a 3-digit site number, the patient numbers will start with this site number followed by a 3-digit patient number starting with 001.

At site, all study personnel (investigator and/or CTA) will be able to perform the randomization as long as this is clearly identified on the Delegation of Authority (DoA).

A patient identification and randomization list will be kept at site.

Blinding

No blinding is applicable in this trial, investigators and patients will know which medications and doses are taken.

Unblinding

Unblinding is not applicable.

Visits

In this trial two kinds of visits are defined: mandatory and optional.

Mandatory visits have to be performed for all included patients while optional visits are recommended but are not obligatory. These can be performed at the investigators discretion. The aim of these optional visits is to check if treatment adaptations have the required effect and for positive reinforcement in view of compliance.

In case patients are randomized, some optional visits are becoming mandatory (see table below) as will be shown in the patient schedule tab of the e-CRF. These visits are important for calculation of secondary outcomes.

Flowchart	Screen	BL	W4	W8	w12	W16	w20	w24	w28	w32	w36	W40	w44	w48	W52	w56	w60	w64
Randomized at W8	X	X	X	X		X		X		X	X	X			X			X
Randomized at W16	X	X	X	X		X	X			X	X	X	X		X			X

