In case NSAIDs or analgesics are used, these should be recorded for effectiveness evaluation, especially in relation to RA and RA related pain.

All study patients must receive oral folic acid supplements of minimally 1mg daily (except on day MTX is taken) as well as Calcium and vitamin D (minimal 1000 mg/800IU daily) as prophylactic treatment.

Trial restrictions

In- and exclusion criteria are clearly describing restrictions on inclusion of patients in the trial.

Assessment of compliance

Medications are prescribed according to the label and will be collected by the patients in their local pharmacy.

At each visit, patients will be questioned about medication intake. In this protocol, patients will be provided with a medication schedule/diary to follow.

In case of increased disease activity, patients will be inquired on their medication intake to pick up possible non-compliance.

9 Pharmacovigilance

Definition of an adverse event

An Adverse Event (AE) is defined as any untoward medical occurrence in a patient administered a pharmaceutical product. The occurrence does not necessarily have a causal relationship with this treatment. An AE can therefore be any unfavorable and unintended sign (including an abnormal laboratory finding), symptom, or disease temporally associated with the use of a medicinal product, whether or not related to the medicinal product.

The investigator and/or his study team will examine any patient experiencing an AE as soon as possible. The investigator will do whatever is medically necessary for the safety and well-being of the patient.

In this trial no adverse events have to be recorded in the e-CRF unless they are categorized as an adverse reaction, related to RA or RA treatment, or as an adverse event of interest as described further in the protocol.

Definition of an adverse reaction (AR)

All untoward and unintended responses to an investigational medicinal product or to an experiment and, when an investigational product is concerned, related to any dose administered.

The phrase "response to an investigational medicinal product" means that a causal relationship between a trial medication and an AE is at least a reasonable possibility, i.e. the relationship cannot be ruled out.

All cases judged by either the reporting medically qualified professional or the Sponsor as having a reasonable suspected causal relationship to the trial medication or to RA qualify as adverse reactions.

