This type of events needs to be recorded in the e-CRF.

Adverse event of interest

Adverse events of interest are defined by the protocol as major cardiac and cerebrovascular events, non-traumatic fractures, malignancies, severe infections, a negative outcome of a pregnancy and death.

Severe infection in the context of an epidemic (e.g.. COVID-19 infection) will also be considered an adverse event of interest and should be reported.

Laboratory Abnormalities:

Abnormal laboratory values will be evaluated by the investigator according to normal practice. Any clinically significant abnormalities should be investigated. If the abnormal value represents an adverse reaction, then this should be recorded in the e-CRF. Other abnormal values will not be recorded in the e-CRF unless considered by the investigator as an adverse event of interest.

Definition of a Serious Adverse Event or Serious Adverse Reaction

All Adverse Events or Adverse Reactions that meet one of the following criteria is considered serious:

- Is Fatal, resulting in death
- Is immediately life-threatening
- Requires inpatient hospitalization or prolongation of existing hospitalization
- Results in persistent or significant disability/incapacity
- Is a congenital anomaly/birth defect

In addition, important medical events that not fulfill above criteria may be considered serious when, based upon appropriate medical judgement, they may jeopardize the patient and may require medical or surgical intervention to prevent one of the outcomes listed in the definition. In this trial no serious adverse events have to be recorded in the e-CRF unless they are categorized as a serious adverse reaction, related to RA or RA treatment, or as a serious adverse event of interest.

Definition of a suspected unexpected serious adverse event (SUSAR)

A serious adverse reaction, the nature or severity of which is not consistent with the information on the experiment, and, when a clinical trial is concerned, with the applicable product information (in this case the patient leaflet joined to the summary of product characteristics as it concerns the use within the label of an authorized product).

This type of events needs to be recorded in the e-CRF.

Collecting and Reporting of adverse events:

All adverse events, whether reported by the patient or noted by study personnel, will be recorded in the patient's medical record and evaluated for causality.

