In this trial only ARs and adverse events of interest, as defined above, will be captured in the e-CRF.

Following rules apply for reporting adverse events in the e-CRF:

- **After informed consent** has been obtained **but prior to initiation of study treatment**, only SAE of interest and ARs caused by a protocol-mandated intervention should be reported
- **After initiation of study treatment**, all ARs, serious adverse reaction (SARs), SUSARs and (serious) adverse events of interest will be recorded in the e-CRF up to the patient's final study visit.

In the e-CRF all above mentioned events will be detailed with the following information:

- Full details in medical terms and case description
- Duration of the event
- The action taken regarding the event
- The outcome of the event
- *Seriousness criteria (medical judgement of the treating investigator):*
 Seriousness will be evaluated for each adverse event based on the criteria described in the paragraph on definition of a serious adverse event. In case the seriousness is answered "yes" than the event should be reported within 24h.
- *Severity Grading for Adverse Events (medical judgement of the treating investigator):*
 Severity should be graded into one of the three classes that describe the clinical severity of the event as it occurred:
 - Mild (does not interfere with daily living)
 - Moderate (somewhat interferes with daily living or medications needed to relieve event)
 - Severe (incapacitating)
- *Causality grading (medical judgement of the treating investigator)*
 Causality should be graded, to determine to what extent the investigator thinks the adverse event is related to the proposed strategy, prescribed drugs or any other protocol-mandated intervention.
- For serious events: whether the event would be considered expected or unexpected according to the Reference Safety Information, which is the current version of the SmPc. *(medical judgement of the treating investigator)*.
- Outcome

Adverse events and reactions should be followed by the investigator until they have returned to normal or stabilized.

All events related to the normal disease course of RA, which are captured within the outcome parameters of the trial, are not considered as adverse events unless these events are considered by the investigator as adverse events of interest.

Reporting of adverse events that meet seriousness criteria:

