Only SARs, SAEs of interest and deaths that occur during this study must be reported to the sponsor. No other SAEs will be reported.

After completion of the seriousness criteria in the e-CRF a SAE-form will automatically appear and should be completed by the investigator. This SAE report will then be electronically signed and automatically e-mailed to the Department of Rheumatology of the University Hospitals Leuven. In case the electronic system is unavailable, a paper copy can be used. Once the e-CRF is again available the information should be added as soon as possible.

The investigator or site must complete this form within 24 hours (immediately) after becoming aware of the SAR or SAE of interest. If the investigator is not available at the time of reporting, the report without causality and expectedness will be provided by site staff within the prescribed timeframe and must be followed-up by medical assessment as soon as possible thereafter.

Follow-up information must be submitted promptly within the electronic template available in the e-CRF.

Staff of the coordinating center will be available to provide guidance regarding SAR or SAE of interest reporting.

Contact Information:

[name]. [name] or [name]. [name]
Department of Rheumatology, University Hospitals Leuven
[name]
[contact]
[contact]
Email addresses: [contact]
[contact]

In case both the CI and [name] are not available, the PM can be contacted:

[name]
Department of Rheumatology, University Hospitals Leuven
[name]
[contact]
[contact]
E-Mail address: [contact]

For this pragmatic strategy trial IMPs are used within the registered label, the chance of encountering a SUSAR is rather low. Nevertheless, in case this would happen, it should be reported within the given timeframe.

The department of Rheumatology of the University hospital Leuven is responsible to report SAEs of interest, SUSARs and deaths to the Competent Authority and Ethical Committees within the defined timelines:

- Immediately in case of death
- 7 days in case of fatal or life threatening SUSAR's
- 15 days in case of all other SUSAR's
- Summary report of all SAR's/SUSAR's annually or final report

Any case of death should also be reported by the investigators to their local Ethical Committee immediately on awareness.

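### Serious events off the events-of-interest list that the open-label investigator judges unrelated are neither captured nor sent to the sponsor, so for these events the exploratory (S)AR comparison depends on unblinded attribution

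*Combined protocol and SAP*

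**What the plan says.** All references are to the combined protocol and SAP.

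- **Who may call an event a reaction** (section 9, *Definition of an adverse reaction*): the class covers "All cases judged by either the reporting medically qualified professional or the Sponsor as having a reasonable suspected causal relationship to the trial medication". Suspected relation with RA itself also qualifies. The threshold is low: a relationship that cannot be excluded is enough.
- **Who grades causality** (section 9, *Collecting and Reporting of adverse events*): "Causality should be graded, to determine to what extent the investigator thinks the adverse event is related to the proposed strategy". The drugs prescribed and other protocol procedures are covered too. This is marked as the treating investigator's judgement.
- **What enters the e-CRF** (section 9, same heading and the SAE definition): adverse reactions and adverse events of interest. Other adverse events, serious or not, stay in the medical record, where they are also evaluated for causality.
- **What goes to the sponsor** (section 9, under the heading on reporting of serious events): the rule is stated as "Only SARs, SAEs of interest and deaths that occur during this study must be reported to the sponsor. No other SAEs will be reported".
- **The list of interest** (section 9, *Adverse event of interest*): major cardiac or cerebrovascular events, together with "non-traumatic fractures, malignancies, severe infections, a negative outcome of a pregnancy and death". The plan adds infections of that kind during an epidemic. The list is defined by type of event, not by cause.
- **Blinding** (section 6): "No blinding is applicable in this trial, investigators and patients will know which medications and doses are taken".
- **The outcome** (section 2): "Side effects: (S)ARs from BL until w104". Section 10 treats it as exploratory, reported with confidence intervals and without a significance test.

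**The concern.** The definition of an adverse reaction provides for two causality opinions, but the reporting rules let only one of them operate on part of the serious events. A serious event that is off the list and judged unrelated at the site does not reach the person who could disagree.

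The remaining opinion comes from an investigator who knows the arm, and it decides whether the event counts in the side-effect outcome. If investigators attribute similar events more readily to one regimen than to the other, the (S)AR counts can differ between arms without a difference in risk, or can hide one. A pattern across sites in events that were each judged unrelated could not be seen in the trial database.

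Infection deserves separate attention. The plan screens for tuberculosis and excludes patients with a history of severe or chronic infection, so it treats infection as a relevant risk. Yet the list names only severe infections, and the severity scale in the same section explains its top grade as incapacitating, separately from the seriousness criteria, which include hospitalisation.

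**Working it through.** **1. Route of a serious event.** Setting the section 9 rules side by side:

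| Serious event | Investigator: related | Investigator: unrelated |
|---|---|---|
| Death | e-CRF and sponsor | e-CRF and sponsor |
| On the list of interest | e-CRF and sponsor | e-CRF and sponsor |
| Off the list | e-CRF and sponsor, as SAR | medical record only |

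Only the last cell is open. For events in that cell the sponsor's power to class an event as a reaction has nothing to act on.

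**2. Is there a backstop?** Section 12 gives the monitor access to source records, to check compliance and accuracy. Omitting an off-list event judged unrelated complies with the protocol, so nothing prompts a query, and no causality re-review is described. Section 2 lists occasional hospitalisation, but under cost-effectiveness and not as part of the side-effect outcome.

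**3. Infection.** If severe carries its meaning from the severity scale, an infection that leads to hospital admission, is graded moderate and is judged unrelated fits neither route. If severe is meant in a general clinical sense, the same infection may be captured. The text does not say which reading applies.

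**4. Illustration.** The plan gives no SAE, AR or attribution rate, so there is no figure to reproduce. The one input from the documents is 104 randomised patients (section 10, sample size table), or 52 per arm. The off-list risk p, equal in both arms, and the attribution probabilities a1 and a0 are assumptions. One event per patient is assumed.

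- Off-list SARs per arm = 52 × p × a
- Apparent ratio = a1 / a0
- Unreported events, both arms = 52 × p × (2 − a1 − a0)

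| p | a1 vs a0 | Off-list SARs | Difference | Ratio | Unreported |
|---|---|---|---|---|---|
| 10% | 0.5 vs 0.5 | 2.6 vs 2.6 | 0 | 1.00 | 5.2 |
| 10% | 0.6 vs 0.4 | 3.1 vs 2.1 | 1.0 | 1.50 | 5.2 |
| 10% | 0.7 vs 0.4 | 3.6 vs 2.1 | 1.6 | 1.75 | 4.7 |
| 10% | 0.8 vs 0.3 | 4.2 vs 1.6 | 2.6 | 2.67 | 4.7 |
| 20% | 0.5 vs 0.5 | 5.2 vs 5.2 | 0 | 1.00 | 10.4 |
| 20% | 0.6 vs 0.4 | 6.2 vs 4.2 | 2.1 | 1.50 | 10.4 |
| 20% | 0.7 vs 0.4 | 7.3 vs 4.2 | 3.1 | 1.75 | 9.4 |
| 20% | 0.8 vs 0.3 | 8.3 vs 3.1 | 5.2 | 2.67 | 9.4 |

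With about 90 randomised (section 5), the counts shrink by 45/52 = 0.87 and the ratios stay the same.

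**5. Why the ratio must not be applied to all SAEs.** Assume a total SAE risk of 20%, so 52 × 0.20 = 10.4 per arm, with half of these on the list. The 5.2 listed events enter the e-CRF in both arms. With attribution of 0.6 vs 0.3, off-list capture is 3.12 vs 1.56. The database then holds 8.32 vs 6.76 serious events, a ratio of 1.23, although the off-list ratio is 2.0.

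**The case against.** The restriction is deliberate and is stated consistently. The trial is classed as low-interventional, the drugs are authorised and used on label, and the stated objective is to evaluate side effects under the rules for marketed products. The attribution threshold is low, relation to RA also qualifies, and causality is graded against the whole strategy rather than etanercept alone. Patients in the standard arm also receive active drugs to which an event can be attributed. That makes large differences in attribution between arms less likely. All adverse events are in the medical record, and the monitor can see them.

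Much of this stands, and it narrows the point. A reader might infer that the sponsor sees no serious event judged unrelated, or that the whole side-effect comparison rests on open-label opinion. The documents do not support either reading: deaths and serious events of interest are reported by type, the sponsor can give its own opinion on them, and they can be compared between arms without regard to cause. A reader might also infer a proven hole in infection capture. That depends on tying the list to the severity scale. The list does not refer to the scale, and the eligibility criteria use the same term without a grade.

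What remains is the off-list event judged unrelated. Low-intervention status may justify light reporting of non-serious events, but it does not reconcile the two-opinion definition with the one-opinion reporting rule. Source access without a review step does not fill the gap.

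**Conclusion.** The point holds for serious events that are off the list and judged unrelated to RA or its treatment. They are not captured or reported, the sponsor cannot judge them, and their absence from the (S)AR comparison is decided by an unblinded investigator. The infection wording is ambiguous and could widen the gap.

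The consequence is limited. The outcome is exploratory, so no confirmatory conclusion changes, but the promised confidence intervals would not reflect differential capture. The direction and size of any bias cannot be derived from the documents. Ratios of 1.5 to 2.7 follow only from the assumed attribution rates and apply only to off-list events, and equal attribution gives 1.0. It would be wrong to read these figures as an expected bias in the trial's safety result. This is a worthwhile, inexpensive improvement.

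**What to change.** 1. In section 9, *Adverse event of interest*, replace severe infections by serious or severe infections, for all patients. A hospitalised infection then counts whatever its grade or attributed cause.
2. In the section 9 rules on SAE recording and reporting, for randomised patients from the randomisation visit to week 104, enter every event that meets a seriousness criterion in the e-CRF and send it to the sponsor whatever the investigator's causality. The sponsor records its own causality.
3. In section 2 and section 10, report all-cause SAEs by allocated arm beside (S)ARs. This count is what takes attribution out of the comparison, since the plan does not describe a blinded sponsor assessment either. It starts at randomisation, where the allocated strategies begin to differ; (S)ARs can still be reported from baseline.
4. For patients already randomised, complete the entries from the medical record, in the same way in both arms. The current version is 4.1 of April 2020 and enrolment was planned from Q2 2018, so without this step capture would differ by calendar time.

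**Cost.** An amendment, an e-CRF change, some retrospective entry and a little more sponsor review. At an assumed total SAE risk of 20% and one event per patient, 104 × 0.20 = 20.8 SAEs in all. Some of these are captured already, so fewer than about 21 extra forms would be needed.
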